2. Moderate physical damage; medical attention needed (e.g., conscious but sleepy, somewhat responsive; second-degree burns; bleeding of major vessel). 3. Moderately severe physical damage; medical hospitalization and likely intensive care required (e.g., comatose with reflexes intact; third-degree burns less than 20% of body; extensive blood loss but can recover; major fractures). 4. Severe physical damage; medical hospitalization with intensive care required (e.g., comatose without reflexes; third-degree burns over 20% of body; extensive blood loss with unstable vital signs; major damage to a vital area). 5. Death Potential Lethality: Only Answer if Actual Lethality=0 Likely lethality of actual attempt if no medical damage (the following examples, while having no actual medical damage, had potential for very serious lethality: put gun in mouth and pulled the trigger but gun fails to fire so no medical damage; laying on train tracks with oncoming train but pulled away before run over). 0 = Behavior not likely to result in injury 1 = Behavior likely to result in injury but not likely to cause death		
less than 20% of body; extensive blood loss but can recover; major fractures). 4. Severe physical damage; medical hospitalization with intensive care required (e.g., comatose without reflexes; third-degree burns over 20% of body; extensive blood loss with unstable vital signs; major damage to a vital area). 5. Death Potential Lethality: Only Answer if Actual Lethality=0 Likely lethality of actual attempt if no medical damage (the following examples, while having no actual medical damage, had potential for very serious lethality: put gun in mouth and pulled the trigger but gun fails to fire so no medical damage; laying on train tracks with oncoming train but pulled away before run over). 0 = Behavior not likely to result in injury 1 = Behavior likely to result in injury but not likely to cause death		eeding of major vessel).
4. Severe physical damage; medical hospitalization with intensive care required (e.g., comatose without reflexes; third-degree burns over 20% of body; extensive blood loss with unstable vital signs; major damage to a vital area). 5. Death Potential Lethality: Only Answer if Actual Lethality=0 Likely lethality of actual attempt if no medical damage (the following examples, while having no actual medical damage, had potential for very serious lethality: put gun in mouth and pulled the trigger but gun fails to fire so no medical damage; laying on train tracks with oncoming train but pulled away before run over). 0 = Behavior not likely to result in injury 1 = Behavior likely to result in injury but not likely to cause death		ct; third-degree burns
extensive blood loss with unstable vital signs; major damage to a vital area). 5. Death Potential Lethality: Only Answer if Actual Lethality=0 Likely lethality of actual attempt if no medical damage (the following examples, while having no actual medical damage, had potential for very serious lethality: put gun in mouth and pulled the trigger but gun fails to fire so no medical damage; laying on train tracks with oncoming train but pulled away before run over). 0 = Behavior not likely to result in injury 1 = Behavior likely to result in injury but not likely to cause death		is over 20% of body:
Potential Lethality: Only Answer if Actual Lethality=0 Likely lethality of actual attempt if no medical damage (the following examples, while having no actual medical damage, had potential for very serious lethality: put gun in mouth and pulled the trigger but gun fails to fire so no medical damage; laying on train tracks with oncoming train but pulled away before run over). 0 = Behavior not likely to result in injury 1 = Behavior likely to result in injury but not likely to cause death		,
Likely lethality of actual attempt if no medical damage (the following examples, while having no actual medical damage, had potential for very serious lethality: put gun in mouth and pulled the trigger but gun fails to fire so no medical damage; laying on train tracks with oncoming train but pulled away before run over). 0 = Behavior not likely to result in injury 1 = Behavior likely to result in injury but not likely to cause death	5. Death	
lethality: put gun in mouth and pulled the trigger but gun fails to fire so no medical damage; laying on train tracks with oncoming train but pulled away before run over). 0 = Behavior not likely to result in injury 1 = Behavior likely to result in injury but not likely to cause death		20. at 16.
before run over). 0 = Behavior not likely to result in injury 1 = Behavior likely to result in injury but not likely to cause death		
0 = Behavior not likely to result in injury 1 = Behavior likely to result in injury but not likely to cause death		am out pulled away
1 = Behavior likely to result in injury but not likely to cause death	The state of the s	
	1 = Behavior likely to result in injury but not likely to cause death	

© 2008 Research Foundation for Mental Hygiene, Inc.

C-SSRS—Since Last Visit (Version 1/14/09)

Page 2 of 2

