- The order of the efficacy assessments evaluated by the Investigator should be the global assessments (e.g., ViSENPsO, s-PGA, PGA-S, CGIC, and CGIS) followed by other efficacy assessments (e.g., mNAPSI, NAPSI, BSA, and PASI).

- To ensure consistency of efficacy assessments over the study duration, it is preferred that the same person/assessor perform the same assessment on the same subject across all visits.
- All study treatments will be administered subcutaneously. All doses of study treatment will be administered at the study center; at home, administration is not permitted.
- All unscheduled visits and assessments performed during the visits will be recorded in the subject's eCRF. During any unscheduled visits, the Investigator will record any AEs and concomitant medications as well as performing any assessments or collecting samples deemed necessary at the discretion of the Investigator.

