Potential Lethality: Only Answer if Actual Lethality=0 Likely lethality of actual attempt if no medical damage (the following examples, while having no actual medical damage, had potential for very serious lethality: put gun in mouth and pulled the trigger but gun fails to fire so no medical damage; laying on train tracks with oncoming train but pulled away before run over). Description			Enter Code	
2 = Behavior likely to result in death despite available medical care				

© 2008 Research Foundation for Mental Hygiene, Inc.

C-SSRS—Baseline (Version 1/14/09)

Page 2 of 2

2) C-SSRS Since Last Visit

COLUMBIA-SUICIDE SEVERITY RATING SCALE (C-SSRS)

Since Last Visit

Version 1/14/09

Posner, K.; Brent, D.; Lucas, C.; Gould, M.; Stanley, B.; Brown, G.; Fisher, P.; Zelazny, J.; Burke, A.; Oquendo, M.; Mann, J.

Disclaimer:

This scale is intended to be used by individuals who have received training in its administration. The questions contained in the Columbia-Suicide Severity Rating Scale are suggested probes. Ultimately, the determination of the presence of suicidal ideation or behavior depends on the judgment of the individual administering the scale.

Definitions of behavioral suicidal events in this scale are based on those used in The Columbia Suicide History Form, developed by [name] and [name], Conte Center for the Neuroscience of Mental Disorders (CCNMD), New York State Psychiatric Institute, [name]. (Oquendo M. A., Halberstam B. & Mann J. J., Risk factors for suicidal behavior: utility and limitations of research instruments. In M.B. First [Ed.] Standardized Evaluation in Clinical Practice, pp. 103-130, 2003.)

For reprints of the C-SSRS contact [name]., New York State Psychiatric Institute, [name]; inquiries and training requirements contact [contact]

© 2008 The Research Foundation for Mental Hygiene, Inc.

C-SSRS Since Last Visit - United States/English - Mapi. C-SSRS-SinceLastVisit_AU5.1_eng-USori.doc

SUICIDAL IDEATION				
Ask questions 1 and 2. If both are negative, proceed to "Suic ask questions 3, 4 and 5. If the answer to question 1 and/or 2			e Last isit	
1. Wish to be Dead Subject endorses thoughts about a wish to be dead or not alive anymore, or wish to fall asleep and not wake up. Have you wished you were dead or wished you could go to sleep and not wake up?			No	
If yes, describe:		-	_	

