Suicidal Behavior: Suicidal behavior was present during the assessment period? Suicide: Answer for Actual Attempts Only Actual Lethality/Medical Damage: 0. No physical damage or very minor physical damage (e.g., surface scratches). 1. Minor physical damage (e.g., lethargic speech; first-degree burns; mild bleeding; sprains). 2. Moderate physical damage; medical attention needed (e.g., conscious but sleepy, somewhat responsive; second-degree burns; bleeding of major vessel). 3. Moderately severe physical damage; medical hospitalization and likely intensive care required (e.g., comatose with reflexes intact; third-degree burns less than 20% of body; extensive blood loss but can recover, major fractures). 4. Severe physical damage; medical hospitalization with intensive care required (e.g., comatose without reflexes; third-degree burns over 20% of body; extensive blood loss with unstable vital signs; major damage to a vital area). 5. Death Potential Lethality: Only Answer if Actual Lethality=0 Likely lethality of actual attempt if no medical damage (the following examples, while having no actual medical damage, had potential for very serious lethality: put gun in mouth and pulled the trigger but gun fails to fire so no medical damage; laying on train tracks with oncoming train but pulled away before run over). 0 = Behavior not likely to result in injury 1 = Behavior likely to result in injury but not likely to cause death		
Suicidal behavior was present during the assessment period? Suicide: Yes No	if yes, describe:	
Suicide: Suicide: Yes No	Suicidal Behavior:	Yes No

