3.3 Analysis Time points

Unless specified otherwise, efficacy and safety endpoints will be analyzed according to their scheduled study visits; unscheduled and early termination visits will be mapped to windowed analysis visits defined by actual study day as in table 1.1 below. If there is no evaluation available from the scheduled study visit, and more than one non-missing evaluation is assigned to an analysis window, the evaluation closest to the target day will be used for the analysis. If the two visits are equidistant from the target day, the earlier visit will be used. For early terminated patients, Part 3 is to start the day of last assessment after the last injection plus 28 days.

The following analysis visit windows will apply:

Table 1.1 Analysis Visit Windows

For: ViSENPsO, NAPSI, mNAPSI, PGA-S, BSA, PASI, and C-SSRS

| Derived Visit | Week | Target Day | Analysis Window |
|---|------|------------|-----------------|
| Part 1: Double-blind Placebo-controlled | | | |

| Effective Date: 10-AUG-2020 | Page 17 of 61 |
|-----------------------------|---------------|

| | _ |
|--|---|
| | |

| _ | |
|-----------------------------|---------------|
| Effective Date: 10-AUG-2020 | Page 18 of 61 |

In particular, NRS pain score will be recorded daily in patient diary for the 7 days leading up to each scheduled visit. The analysis visit for NRS will be assigned the same as for the subsequent visit according to Table 1.1, ie, as 7 consecutive days prior to that visit. In the event of a missed visit, the available NRS scores will be mapped to an analysis visit according to Table 1.1, using the last diary entry date as anchor. Any NRS entries outside of the 7-day window will be excluded from the calculation of average NRS. At least 4 out of the 7 daily records are required to calculation of average.

All other assessments (ECG, laboratory data) will be analyzed according to the assigned (nominal) visit unless otherwise specified.

[figure not shown]
For any events/assessments on or after the first administration of study drug, study day is calculated as: event/assessment date – date of first administration of study drug + 1. As such, Day 1 is defined as the date of first administration of study drug.

For any events/assessments before the first administration date, study day is calculated as event/assessment date – date of first administration of study drug.

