Change in binary response to the questions from no to yes in any questions will be summarized in a shift table describing baseline vs post-baseline per visit, and worst post-baseline overall. Categorical scores will be analyzed similarly. C-SSRS risk levels are also summarized by visit. Results from the C-SSRS will be listed by subject. Results to Week 28 will be described in the Part 1 analysis, and overall results to Week 52 will be described in the final analysis.

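### The SAP's one-form-per-window rule can leave a positive C-SSRS form out of the by-visit tables when a negative form shares its window

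*Protocol*

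**What the plan says.** **SAP 3.3 (Analysis Time points).** The heading of Table 1.1 names the instruments under the windowing rule: "For: ViSENPsO, NAPSI, mNAPSI, PGA-S, BSA, PASI, and C-SSRS". Visits outside the schedule are not thrown away: "unscheduled and early termination visits will be mapped to windowed analysis visits defined by actual study day". A scheduled evaluation has priority. The tie-breaking rule starts from the condition "If there is no evaluation available from the scheduled study visit, and more than one non-missing evaluation is assigned to an analysis window"; in that case "the evaluation closest to the target day will be used for the analysis", and an equidistant pair goes to the earlier visit. The section is a default that other sections may override. It has no worst-value rule. The window limits themselves are not legible in the text supplied.

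**Protocol.** Note n to the Schedule of Activities and section 8.2.3 require the Since Last Visit version at every post-baseline visit. Appendix 19 reproduces it, labelled "2) C-SSRS Since Last Visit", and its summary behaviour item reads "Suicidal behavior was present during the assessment period". The last scheduled C-SSRS is at Week 52; none is planned at Week 72. Under section 8.0, the investigator at an unscheduled visit records adverse events and medications, as well as "performing any assessments or collecting samples deemed necessary at the discretion of the Investigator".

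**SAP 10.6 (Other Safety Parameters).** Item responses go into shift tables per visit and for the worst post-baseline value overall, and the scores are treated likewise. For risk level, "C-SSRS risk levels are also summarized by visit". Results are also listed by subject. Nothing says which forms enter the worst post-baseline value.

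**Parallel reporting.** Protocol 8.3.7 makes depression, suicidal ideation and other behaviour events Events of Clinical Interest (ECIs). SAP 2.3.4 makes the percentage of subjects with an event of clinical interest a safety endpoint, and SAP 10.1 tabulates and lists ECIs.

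**The concern.** Selecting one evaluation per window is sensible for mNAPSI or PASI. Two readings a week apart describe the same slowly changing state, and the one nearer the target day is the better estimate for that visit. A Since Last Visit form is not a reading of a state. It is a report on an interval, and the next form starts where it ended. Setting one of two forms aside therefore removes an interval from the by-visit record, and a later form need not recover it.

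The selection takes no account of the answer. Where a positive and a negative form compete, the negative one is kept whenever it is the scheduled form or the closer one. Change from baseline in C-SSRS results is a named safety endpoint in SAP 2.3.4, so its tables should not depend on which day a form happened to be completed.

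**Working it through.** The plan states no figure here, so there is nothing to reproduce. The check is to apply the written rule to constructed sequences of forms.

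*Inputs from the documents:* scheduled form first; otherwise the form closest to the target day; ties to the earlier form (SAP 3.3). Scheduled C-SSRS visits at Weeks 4, 8 and 12 (Schedule of Activities).

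*Assumptions, because the Table 1.1 rows are not legible:* target day = 7 × week + 1, giving Days 29, 57 and 85 for Weeks 4, 8 and 12. Windows split at midpoints, so the Week 8 window runs from about (29 + 57)/2 = Day 43 to (57 + 85)/2 = Day 71. A positive form is given an ideation score of 4 (some intent to act); all other forms score 0.

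| Pattern | Forms around Week 8 | Form used by visit | Positive form shown by visit? | Worst over all forms | Worst over selected forms |
|---|---|---|---|---|---|
| A | Scheduled Day 57 negative; unscheduled Day 64 positive | Day 57 at Week 8 | No | 4 | 0 |
| B | Scheduled Day 57 negative; early termination Day 80 positive | Day 80 at Week 12 | Yes | 4 | 4 |
| C | Scheduled Day 57 negative; early termination Day 66 positive | Day 57 at Week 8 | No | 4 | 0 |
| D | Week 8 visit missed; unscheduled Day 57 negative and Day 66 positive | Day 57 at Week 8 | No | 4 | 0 |
| E | Week 8 visit missed; unscheduled Day 60 positive | Day 60 at Week 8 | Yes | 4 | 4 |
| F | Week 8 visit missed; unscheduled Day 58 positive and Day 66 negative | Day 58 at Week 8 | Yes | 4 | 4 |

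Three results follow.

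1. The positive form is left out of the by-visit table in A, C and D and kept in B, E and F. What separates them is whether a scheduled or closer negative form sits in the same window. These are constructed patterns; 3 of 6 is not a rate.
2. In A, C and D the worst post-baseline score is 4 or 0 depending on whether all forms or only the selected forms are used. SAP 10.6 leaves that open, so two programmers could follow the SAP and report different values.
3. If the worst answer in each window is taken, all six patterns show the event by visit.

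*Risk level.* SAP 10.6 defines high risk as a yes to ideation Question 4 or 5, or any positive behaviour answer. That is an ideation score of at least 4 or a behaviour score above 0, so the worst risk level follows from the worst scores once their source is settled.

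*Size of one event.* One subject is 1/48 = 2.1 percentage points of a planned arm.

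**The case against.** Four points can be made for the plan as it stands.

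- **Parallel capture.** Suicidal ideation and behaviour events are ECIs, tabulated and listed by rules that do not use the windows. This stands. It rules out any reading in which the event vanishes from the report. It does not correct the C-SSRS tables, which could then disagree with the ECI tables.
- **A worst-value summary is already planned.** SAP 3.3 is only a default, and an overall worst value is reasonably read as covering every form. That is probably the intention, but the SAP does not say so, and the by-visit tables are unaffected either way.
- **Competition within a window may be uncommon.** Unscheduled C-SSRS forms are discretionary. An early-termination form, due about four weeks after the last dose, will often be alone in its window and so be kept. This stands, and it is why no frequency is claimed.
- **The intervals may overlap.** The documents do not say whether a discretionary form at an unscheduled visit restarts the recall period. If it does not, the next scheduled form reaches back over the event and should record it, which would rescue patterns A and D in a later window. The natural reading of Since Last Visit is that recall does restart. Pattern C does not depend on this, because no further C-SSRS is scheduled after the termination form.

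**Conclusion.** The point holds as a conditional defect in SAP 3.3 and a gap in SAP 10.6. Followed as written, the rule lets a negative form displace a positive one in the by-visit C-SSRS item, score and risk-level tables whenever the negative form is the scheduled or closer one in the same window. The error for such an event runs towards understatement. The fault is in those two SAP sections; the form item in Protocol Appendix 19 is standard and needs no change.

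A reader might infer more, and the documents do not support it. They do not show that every positive unscheduled or early-termination form is dropped, since such forms are mapped to windows and used when nothing competes. They do not show that the suicidality signal is lost, given the ECI tables, the planned worst-value summary and the by-subject listing. Nor do they allow a rate. Assuming 90–95% attendance at scheduled visits and concluding that 90–95% of unscheduled forms are set aside only restates the assumption, under window limits that cannot be seen. It also says nothing about how many such forms would be positive.

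The conclusion rests on recall generally restarting at each form, and on Table 1.1 carrying no special C-SSRS rule in its illegible rows. Severity is minor: descriptive safety tables only, with no effect on efficacy results, sample size or type I error.

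**What to change.** Two sentences in the SAP.

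- **SAP 3.3:** exempt the C-SSRS from the closest-to-target selection. For each analysis visit, combine the scheduled form with any unscheduled or early-termination forms mapped to that window by taking the worst answer per item, and derive the scores and risk level from the combined answers.
- **SAP 10.6:** state that worst post-baseline is taken over every post-baseline form, whether or not it was selected for a window.

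A worst post-baseline row in the risk-level table is optional, since high risk can be derived from the worst scores.

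The cost is one changed derivation. No new data are needed, and the change can be made without knowledge of treatment assignment.

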Appendix 20: static Physician's Global Assessment (s-PGA):

	*Induration	^a Erythema	Scaling
	(averaged over all lesions)	(averaged over all lesions)	(averaged over all lesions)
0	No evidence of plaque elevation	No evidence of erythema; hyperpigmentation may be present	No evidence of scaling
1	Minimal plaque elevation (≈ 0.5 mm)	Faint erythema	Minimal, occasional fine scale over less than 5% of the lesions
2	Mild plaque elevation (≈ 1 mm)	Light red coloration	Mild, fine scale predominates
3	Moderate plaque elevation (≈ 1.5 mm)	Moderate red coloration	Moderate, coarse scale predominates
4	Marked plaque elevation (= 2 mm)	Bright red coloration	Marked, thick, non- tenacious scale predominates
5	Severe plaque elevation (= 2.5 mm or more)	Dusky to deep red coloration	Severe, very thick tenacious scale predominates

Static Physician's Global Assessment Score (averaged over all lesions):		
0 = clear, except for residual discoloration		
1 = almost-clear, lesions have individual scores for induration" erythema and scaling (IES) of at lea	st 1	
2 = Lesions have individual scores for IES of at least 2		
3 = Lesions have individual scores for IES of at least 3		
4 = Lesions have individual scores for IES of at least 4		
5 = Lesion's have individual scores for IES of at least 5		

Note: When required for comparison purposes, we converted the sPGA numerical range of 0 to 5 to clear = 0, almost-clear = 1, mild = 2, moderate = 3, marked = 4, and severe = 5.

Reference: Chow C, Simpson MJ, Luger TA, Chubb H, Ellis CN. Comparison of three methods for measuring psoriasis severity in clinical studies (Part 1 of 2): change during therapy in Psoriasis Area and Severity Index, Static Physician's Global Assessment and Lattice System Physician's Global Assessment. J Eur Acad Dermatol Venereol. 2015 Jul;29(7):1406-14.

Appendix 21: Clinician Global Impression of Change (CGIC)

Please choose the response below that best describes the overall change in your patient's nai
psoriasis since he/she started taking the study medication.
□ Much better
□ A little better
□ No change
□ A little worse
□ Much worse

